### **A/LCI Module**

The centerpiece of LCI instrumentation is an interferometer, in which light from a known reference distance is combined with light returning from the probe. For the mapping and sizing modes in our

system, two separate interferometers are provided. The interferometer used for the sizing mode is the a/LCI module described in this section. The a/LCI module is a fully integrated prototype a/LCI system. The module includes a fiber-optic probe encased in a polymer sheath, which we refer to as the a/LCI catheter.

The a/LCI module contains a light source, which is a superluminescent diode (Superlum, Moscow, Russia) emitting infrared light at wavelengths between 815 and 845 nm. The total power of the SLD at its output is approximately 25 mW, but the amount of power delivered by the a/LCI catheter is reduced. The power at the output of the a/LCI catheter is limited to less than 4 mW.

The tip of the a/LCI catheter is fixed within the scanning handle. The illumination and detection beams provided by the catheter are scanned as described in the optical probe section.

The a/LCI module also contains a spectrometer, a device that measures the interference signal by wavelength. The spectrometer output is communicated by USB to a host computer. Additionally, the module contains circuitry that controls and synchronizes the behavior of the spectrometer, illumination shutter, and reference stepper motor (for altering the optical path length of the reference arm).

A metal housing encloses the a/LCI module. A single power and USB connection are provided on a rear panel that serves all enclosed devices. A front panel power button allows the entire module to be powered on and off simultaneously.

Several optical fibers pass from the a/LCI module to the OCT module. These fibers carry illumination and signal light to and from the a/LCI light source, the optical probe, and the OCT module spectrometer.

### **OCT Module**

The OCT module contains the interferometer to produce OCT images during the mapping mode of a scanning a/LCI procedure. The OCT module does not contain an independent light source. A fiber from the a/LCI module delivers light into the OCT module, where illumination light passes through an optical circulator and is returned to the a/LCI module to be inserted into the a/LCI catheter. Light backscattered by the sample returns via the a/LCI catheter along the same fiber, and returns to the OCT module circulator. The circulator redirects the backscattered light to a fiber coupler within the OCT module, where it combines with light from a reference arm (also within the OCT module) and is detected by an OCT spectrometer. The spectrometer is served by its own power supply and USB connection to the host computer.

### **Electronic Control Module**

Several circuit boards and devices are mounted within the physical enclosure for the purpose of controlling and supplying power to the components within the scanning handle. A controller for the stepper motor receives power from its own power supply and communicates via USB to the host computer. Several insulated wires connect the stepper motor controller to the scanning handle. Another device controls and powers the scanning mirror in the scanning handle. This unit also receives its own power and USB connection to the host computer, and is connected to the scanning mirror in the handle via a multi-conductor cable.

## Computer

A small form factor computer (VivoMini, ASUS, Taipei, Taiwan) performs the data acquisition and control through a custom application in Labview (National Instruments, Austin, TX). Real-time display of the white-light endoscopic images is provided, as well as synchronized acquisition of OCT and a/LCI data from spectrometers. The data from both mapping modes and sizing modes are stored on the encrypted hard drive.

## Physical enclosure

The a/LCI module, OCT module, electronic control module, and computer are situated upon a wheeled steel cart. Power to all components is provided through standard 120V mains routed through a medical-grade isolation transformer.

## Stage 2 Study Procedures for subjects at Duke

Each subject will attend 1 study visit that will last about 1 hour and include the following procedures.

- Read consent form
- Ask / answer questions
- Sign consent form
- Complete brief medical questionnaire to determine eligibility
- Urine pregnancy test – must be negative before imaging can occur
- Scanning a/LCI examination of the cervix (without speculum)
- Scanning a/LCI examination of the cervix (with speculum) – only if necessary

We will obtain written informed consent and confirm eligibility criteria. Data collection will include a brief medical history and pregnancy testing. Participants will be interviewed one-on-one to complete the questionnaire regarding medical and reproductive history. The nurse or doctor will then perform the LCI study measurements.

The nurse or doctor will gently place the scanning a/LCI probe against the cervix. Lubricant will be placed on the outside of the probe for subject comfort. White light camera visualization, incorporated into the scanning a/LCI probe, will guide the probe positioning by the clinician to confirm contact with the cervical epithelium. Up to 4 minutes will be allotted for probe manipulation for optimal contact. The probe will then be held in place for scanning a/LCI data acquisition for up to 2 minutes. When data collection is completed, or permitted time is elapsed, the scanning a/LCI probe will be removed and placed on a custom holder that prevents the contact portions of the probe from coming into contact with contaminating surfaces.

If the nurse or doctor could not obtain a good view of the cervix using the integrated white light camera, they may choose to insert a speculum for direct visualization of the cervix. The scanning a/LCI probe will again be placed against the cervix with 4 minutes allotted for probe manipulation and 2 minutes for scanning a/LCI measurements.

## **Stage 2 Study Procedures for subjects at Jacobi**

Subjects will be women presenting to the clinic for evaluation after an abnormal cytology result. Subjects will be informed of the study when they present to the clinic. If interested in participating, subjects will complete the following study-related procedures in addition to the standard of care visit procedures.

- Read consent form
- Ask / answer questions
- Sign consent form
- Urine pregnancy test – must be negative before imaging can occur
- Scanning a/LCI examination of the cervix (with speculum)

We will obtain written informed consent and confirm eligibility criteria. Data collection will include a brief medical history and pregnancy testing.

The doctor will then insert a speculum in order to directly visualize the cervix. The cervix may or may not be wiped clear to aid visibility if necessary. The doctor will then gently place the scanning a/LCI probe against the cervix. White light camera visualization, incorporated into the scanning a/LCI probe, will guide the probe positioning by the clinician to confirm contact with the cervical epithelium. The probe will then be held in place for scanning a/LCI data acquisition for up to 2 minutes. When data collection is completed, the scanning a/LCI probe will be removed and placed on a custom holder that prevents the contact portions of the probe from coming into contact with contaminating surfaces.

The doctor will then continue with the standard of care portion of the visit (including collection of cervical biopsies).

## **Selection of Subjects**

This project will recruit healthy women who:

- are able to provide informed consent
- are at least 21 years old
- are willing to abstain from sexual intercourse for at least 24 hours before the study visit

Participants meeting any of the following exclusion criteria will be excluded from taking part in this study. Women must not:

- be pregnant
- have a current gynecologic infection or discharge
- have had any cervical surgery
- have had medical or cosmetic surgery involving the reproductive organs or genitals within the past 6 months
- be currently enrolled in any research studies involving the application of vaginal formulations
- be employed or supervised by the study investigators
- have any other condition that, in the opinion of the study clinician, would contraindicate participation in the study

In addition, to participate in stage 1 (mLCI device development) at the Duke site, women must not:

- have given birth to a baby
- be using an IUD

To participate in Stage 2 (scanning a/LCI device development) at the Jacobi site: subjects will be recruited from women who present to the clinic for evaluation for abnormal cytology. The study will recruit women with no prior history of cervical surgical procedures.

## Subject Recruitment

### Subject Recruitment at Duke

Duke will recruit up to 15 women to enroll in stages 1 and 2 of the study, in order to achieve the target number of 10 subjects who complete each stage. This gives a total enrollment of up to 30 subjects at Duke to complete both stages of the study at that site.

The study will be advertised on the ResearchMatch website, the DukeList website, and/or flyers posted around campus. Recruiting will be managed by our study coordinator. The inclusion of minorities in the group of women recruited will reflect the local distribution in the Durham area.

After learning about the study, prospective subjects will call the study coordinator for more information. During this telephone call, the study coordinator will state the study requirements plus a brief description of the procedures. If the prospective subject is interested in participating in the study, a study visit will be scheduled. The prospective subject's contact information will be kept in a locked desk or file cabinet or password protected file in the study coordinator's office. If the prospective subject states that she does not qualify or is not interested in participating, the contact information will be destroyed.

### Subject Recruitment at Jacobi

Potential subjects will be informed of the study when they present to the clinic for a regular clinical care visit.

Jacobi will enroll up to 100 women for stage 1, in order to achieve the target number of 40 women who complete stage 1. For stage 2 of the study, up to 140 women will be recruited in order to enroll 70 participants in this cross-sectional study (50 HIV-negative participants and 20 HIV-positive participants). The goal distribution of participants in this study is approximately 14 women with normal histology, 21 women with CIN-1, 14 women with CIN-2 or CIN-2/3, 14 women with CIN-3, and 7 women with invasive cancer.

## Consent Process

The study coordinator will conduct the consent process. The consent process will be conducted at a meeting in a private office or other suitable private location (consult room, conference room). To ensure privacy during the meeting, the door will be closed. Thirty minutes will be allocated for conducting the initial consent discussion, allowing time for the prospective subject to read the consent form and ask any questions she may have. The prospective subject can choose to sign the consent form at that time, or take more time to decide if she wishes. The prospective subject will have as much time as she needs

to decide whether or not to participate. However, enrollment will continue, and if all study slots are full by the time the prospective subject decides to participate, she may not be enrolled in the study. The prospective subject may ask questions at any time by contacting the study coordinator or PI.

To minimize the possibility of coercion or undue influence, study personnel will inform subjects of their rights as a research participant, including their right to refuse to participate or to withdraw from the study at any time without penalty. Duke students and employees under direct supervision of the study staff will not be allowed to participate in this study.

## Subject's Capacity to Give Legally Effective Consent

Subjects who do not have the capacity to give legally effective consent will not be included in this study.

## Risk / Benefit Assessment

### Risk/Benefit Assessment of the study in general

#### ***Potential Risks***

Potential risks include:

1. breach of confidentiality
2. coercion
3. discomfort with the nature of the research
4. side effect from study procedures and/or devices

#### ***Potential Benefits***

There is no direct benefit to subjects participating in this research study. However, the novel LCI devices to be developed in this proposal would potentially advance the management of cervical dysplasia by assisting clinical decision-making without relying on gross colposcopic impression. The current proposal is to conduct the early feasibility studies necessary for technology development. Data will also be collected about epithelial characteristics as visualized by LCI, which could improve our understanding about the basic biology of the cervical epithelium. The long-term goal is to develop devices that could be incorporated into routine clinical care. The LCI device could provide real-time information to the clinician and reduce the number of clinical visits needed.

## ***Alternative Treatments***

There are no alternative treatments to participating in this research. It is not intended to be therapeutic, but to acquire basic scientific knowledge.

### Risk Assessment and Risk Minimization for Study Activities

#### ***Potential Risks***

Potential risks include:

1. breach of confidentiality
2. coercion
3. discomfort with the nature of the research
4. side effects from study procedures and/or devices

### ***Breach of Confidentiality***

Subjects will provide personal information, including sexual history and health information. Breach of confidentiality will be avoided by training research staff in the protection of human subjects and by coding and limiting access to data. Each participant will be assigned a research subject number. The only documents linking the subject's identity with her subject number will be the consent form and the enrollment log. The contact information list and payment request forms will contain the subject's identity only. The medical questionnaire, pregnancy test result, and data spreadsheets will reference the subject number only. The subject's social security number, required on the payment request form, will be removed once payment has been processed. Once the study is complete, all contact information will be deleted, unless the participant requests to be contacted for future studies conducted by [name] or his colleagues. All of the participant's study documents will be kept in a locked file cabinet in the study coordinator's office. Databases containing PHI will be maintained on a password-protected computer with full disk encryption.

### ***Coercion***

Coercion occurs when potential participants feel compelled to participate in research for reasons such as perceived demand or the availability of large sums of reimbursement. This can be particularly true when there is little benefit to the individual for their participation. In this study, there is minimal risk of coercion as personnel will inform subjects of their rights as a research participant, including their right to refuse to participate or to withdraw from the study at any time without penalty. Reimbursement is not believed to be coercive, based on the time required and the nature of the research. The amount of reimbursement is comparable to similar studies.

### ***Discomfort with the Nature of the Research***

Participants may feel discomfort with the personal nature of this research. Before the participant is enrolled in the study, detailed study procedures will be explained so she is aware of what the research entails. Subjects will provide personal information, such as sexual health and history. Some study procedures will be conducted with the physician/nurse and research assistant/chaperone in the room, including insertion of the LCI devices into the vagina by the physician/nurse (similar to a pelvic exam) and making measurements with the devices. Participating in these research procedures and providing personal information may be uncomfortable for some women. It is unlikely this discomfort will result in any serious adverse events. Should participants report discomfort with the research, they will be reminded of their rights to not participate in the study or to withdraw from the study at any time. Subjects may contact the principal investigator or one of the study physicians at any time to discuss questions or concerns about the study.

### ***Side Effects from Study Procedures and/or Devices***

Risks of the LCI Devices: The LCI devices will be handled gently for placement against cervical tissue. We expect very minimal risk for tissue abrasion or irritation as the devices will have a smooth plastic and silicone surface and commercial gynecological lubricant will be applied before cervical contact. The devices will be cleaned in full accordance with high level disinfection clinical procedures at DUHS. Specifically, probes will be enclosed in a Trophon EPR high-level disinfection system to disinfect all external surfaces. Study staff will complete training and competency reviews per institutional procedures. For the LCI technique, a fiber optic bundle transmits near infrared light onto the epithelia to image the cervix. The light source has been either certified for medical use or tested to demonstrate that it complies with medical safety standards.

## Costs to the Subject

There will be no costs to the subject as a result of participating in this study.

## Data Analysis & Statistical Considerations

### Data Analysis & Statistical Considerations

#### ***STAGE 1: mLCI device development***

##### ***Data analysis for Duke site***

The proposed study is designed as a pilot study, intended to provide feasibility and usability data to inform future studies on a larger scale. The planned pilot study will include 10 subjects, which will yield success/failure metrics of the probe design with 10% precision. Elements of the probe performance that will be evaluated include ease of use by the medical practitioner, patient comfort, ability to access the relevant anatomy, and quality of mLCI imaging data. Because the goal of the pilot study is the evaluation of general feasibility, no subject data will be excluded if no predetermined exclusion criteria are met.

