[name], the Duke PI of this study, is the primary awardee of the NIH grant supporting this work. [name] and his team have developed the LCI research devices and will conduct small studies at Duke (described below) to assess if any adjustments to the devices are needed before they are sent to Jacobi Medical Center for the larger studies. The studies at Jacobi Medical Center will be funded as a subaward / consortium agreement of [name] NIH grant.

Duke will recruit up to 15 women to enroll in stages 1 and 2 of the study, in order to achieve the target number of 10 subjects who complete each stage. This gives a total enrollment of up to 30 subjects at Duke to complete both stages of the study at that site.

Jacobi will enroll up to 100 women for stage 1, in order to achieve the target number of 40 women who complete stage 1. For stage 2 of the study, Jacobi will enroll up to 140 women in order to achieve the target number of 70 women who complete that stage.

Data from both sites will be analyzed at Duke. Study conduct at Duke will be under the oversight of the IRB of the Duke University Health System. Study conduct at Jacobi Medical Center will be under the oversight of the IRB of the Albert Einstein College of Medicine and Montefiore Medical Center.

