Insertion method	Criteria	Time for probe placement	Time for mLCI acquisition	Maximum total time
Without speculum	All patients	4 min	1 min	5 min
With standard speculum	All patients	4 min	1 min	5 min
With alternate speculum	Optional (only if standard speculum not satisfactory AND practitioner believes alternate may achieve better result)	4 min	1 min	5 min

Comparing measurements made by inserting the mLCI device with and without a speculum will allow us to determine if the white light visualization by the camera is sufficient to correctly place the probe over the cervix without having to use a speculum in future studies. The ability to use an alternate in the event that a conventional speculum does not permit adequate mLCI probe placement will also inform our selection of the type of speculum, if any, that is most suited for subsequent studies.

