#### ***STAGE 2: scanning a/LCI device development***

##### ***Data analysis for Duke site***

The proposed study is designed as a pilot study, intended to provide feasibility and usability data to inform future studies on a larger scale. The planned pilot study will include 10 subjects, which will yield

success/failure metrics of the probe design with 10% precision. Elements of the probe performance that will be evaluated include ease of use by the medical practitioner, patient comfort, ability to access the relevant anatomy, and quality of scanning a/LCI imaging data. Because the goal of the pilot study is the evaluation of general feasibility, no subject data will be excluded if no predetermined exclusion criteria are met.

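### Ten subjects per Duke stage do not give 10% precision for a success rate: the figure matches the 1/10 step between results, not a margin of estimation

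*Combined protocol and SAP*

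**What the plan says.** Under Data Analysis & Statistical Considerations, the Stage 1 subsection for the Duke site says: "The planned pilot study will include 10 subjects, which will yield success/failure metrics of the probe design with 10% precision". The Stage 2 subsection for Duke repeats this ("The planned pilot study will include 10 subjects, which will yield" and then "success/failure metrics of the probe design with 10% precision"). It is the only numerical justification for 10 subjects in either stage.

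Both subsections describe a pilot for feasibility and usability that is meant to inform larger studies. On what will be judged, the Stage 1 text says: "Elements of the probe performance that will be evaluated include ease of use by the medical practitioner, patient comfort, ability to access the relevant anatomy"; imaging data quality completes the list. Purpose of the Study allows up to 15 women to be enrolled per stage "in order to achieve the target number of 10 subjects who complete each stage".

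No section defines precision, or gives a confidence level, interval method or expected success rate for the Duke metrics. The other 10% figures, in the Jacobi analysis sections, are limits on error in area or T-zone mapping, so they do not supply the missing definition. The only significance level, 0.05, is for p-values and appears in the Jacobi Stage 2 analysis.

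**The concern.** Precision of a success rate is ordinarily read as a margin: how far the true rate may lie from the observed one. Read that way, the sentence promises that 10 women fix a success rate to within about 10 points, which 10 binary observations cannot do at a conventional confidence level.

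What is at stake is how the pilot rates will be read. Because the data are to inform larger studies, a reader who trusts the figure could take 9 successes in 10 to mean roughly 80% to 100%. The data would not exclude a rate little better than one in two.

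**Working it through.** **Inputs.** n = 10 and the stated 10% come from the two Duke analysis subsections. The plan gives no confidence level, so 95% is an assumption, with 90% and 80% shown beside it. No success rate is given, so every result from 0/10 to 10/10 is covered.

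**1. Reproducing the plan's figure.** With 10 subjects, an observed proportion can change only in steps of 1/n = 1/10 = 10 percentage points. This matches the stated figure exactly.

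**2. The figure as a confidence margin.** For x successes in n, the exact (Clopper-Pearson) limits are

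- lower L = the α/2 quantile of Beta(x, n − x + 1), with L = 0 if x = 0;
- upper U = the 1 − α/2 quantile of Beta(x + 1, n − x), with U = 1 if x = n.

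Half-width = (U − L)/2. For 10/10 at 95%, L = 0.025^(1/10) = 0.6915, so the half-width is (1 − 0.6915)/2 = 15.4 points.

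| Result | Exact 95% interval | Half-width 95% | 90% | 80% |
|---|---|---|---|---|
| 5/10 | 18.7%–81.3% | 31.3 | 27.8 | 23.3 |
| 6/10 | 26.2%–87.8% | 30.8 | 27.3 | 22.9 |
| 7/10 | 34.8%–93.3% | 29.3 | 26.0 | 21.8 |
| 8/10 | 44.4%–97.5% | 26.5 | 23.5 | 19.8 |
| 9/10 | 55.5%–99.7% | 22.1 | 19.5 | 16.3 |
| 10/10 | 69.2%–100% | 15.4 | 12.9 | 10.3 |

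Results below 5/10 mirror these. No exact half-width at 95%, 90% or 80% is 10 points or less. Half-widths also flatter the extreme results: at 10/10 the whole 95% interval lies on one side of the estimate, and its limit is 100 − 69.2 = 30.8 points away.

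**3. Other interval methods at 95%.** The half-width is 13.9 to 26.3 points by Wilson, 16.0 to 26.3 by Agresti-Coull and 10.9 to 27.7 by Jeffreys. By Wald it is 18.6 to 31.0 for 1/10 to 9/10; its zero width at 0/10 and 10/10 is degenerate.

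**4. The figure as one standard error.** SE = √(p(1 − p)/10).

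- p = 0.9: √(0.09/10) = 9.5 points
- p = 0.8: √(0.16/10) = 12.6 points
- p = 0.5: √(0.25/10) = 15.8 points

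SE is 10 points or less when p(1 − p) ≤ 0.1. Solving p(1 − p) = 0.1 gives p = (1 ± √0.6)/2, that is 0.887 or 0.113. This reading therefore needs a true rate of at least 88.7% or at most 11.3%, and the plan states no expected rate.

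**The case against.** The strongest reply is that the sentence never mentions a margin, an interval or a confidence level. It speaks of success/failure metrics from 10 subjects, and those do move in tenths, so the figure is right on its likeliest reading. The 95% level comes from this review. There are also readings under which 10 points or less is attained: one standard error when success is about 90% (9.5 points), or looser intervals at 0/10 and 10/10 (Wilson at 80% gives 7.1 points, Jeffreys at 90% gives 8.5).

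Much of this stands. The step does equal 10%, the confidence level is assumed, and it would be wrong to say that no reading yields 10 points. But a step between possible results is not the precision of an estimated rate, and the text does not say that a step is meant. The favourable readings need a particular success rate, or an extreme result with a looser interval, none of which the plan states.

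A reader might infer three stronger points that the documents do not support.

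- **That the pilots are too small.** Nothing in the plan requires a 10-point margin. The stated goal is general feasibility, for which 10 subjects can be reasonable.
- **That non-completers will be dropped and success rates inflated.** The 15-for-10 allowance invites this, but consent is signed before the eligibility questionnaire and the pregnancy test, so the extra places can cover women who are never imaged. Placement attempts are time-limited, so a failed placement can still end in a finished visit. The rule that "no subject data will be excluded if no predetermined exclusion criteria are met" also points towards keeping failures in.
- **That the optional speculum attempts break the figure.** They do apply only to some women ("only if standard speculum not satisfactory AND practitioner believes alternate may achieve better result" in Stage 1; "they may choose to insert a speculum for direct visualization of the cervix" in Stage 2). But they are fallbacks, and the Duke analysis sections do not name them as separate metrics. How many women would have them is unknown.

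**Conclusion.** The sentence is wrong as a statement of estimation precision, in both Duke stages. At n = 10 the exact half-width is 1.5 to 3.1 times the stated 10 points at 95% (15.4/10 and 31.3/10), and it exceeds 10 points for every result even at 80%. The conclusion rests on reading precision as the uncertainty of an estimated rate, with the 95% level assumed. That the author meant the 1/10 step is an inference, though a likely one.

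Severity is minor. No go/no-go rule and no Jacobi benchmark depends on the figure, and the plan already calls each Duke study a pilot. Definitions of success for each metric and separate denominators for optional attempts would be useful detail, but they are side notes and not part of this finding.

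**What to change.** Keep 10 subjects. In the Duke analysis subsections for Stage 1 and Stage 2, replace the precision sentence with wording such as:

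> With 10 evaluable subjects, observed success rates change in steps of 10 percentage points; the exact 95% CI would be 44.4%–97.5% for 8/10, 55.5%–99.7% for 9/10 and 69.2%–100% for 10/10.

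Add that each success/failure rate will be reported with its denominator and an exact 95% interval.

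The cost is one sentence replaced in two places, and a denominator and interval beside each reported rate. No subjects are added, and no study procedure or Jacobi analysis changes. The only downside is that the stated precision looks less favourable.
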